The primary treatment for BCLM remains chemo-therapy and, more recently, targeted immunotherapy. Liver metastases from other primary tumors, such as colorectal cancers, are routinely resected as part of standard management. Breast cancer rarely develops isolated liver metastases because neo-plastic cells at this stage have often already reached systemic circulation with the possibility of further localization, unlike colon cancer, where the liver, through the portal system, is the first organ to be colonized. Therefore, the role of liver resection in BCLM remains controversial [6-8].

Hepatic resection and/or ablation was not associated with a survival advantage in some studies [9], whilst in other disclosed a remarkable improvement as compared to systemic treatment alone [10,11], thus indicating surgical intervention as suggested in highly selected patients with the goal of providing time off of systemic chemotherapy.

Our study thus aims to provide further insights in this complex and still unclear field of research.

OBJECTIVES

Primary Objective

Primary aim of the study is to compare the efficacy of liver resection vs. medical therapy alone in Breast Cancer Liver Metastasis (BCLM) patients.

Secondary Objectives

- To assess the recurrence rate after liver resection or medical treatment alone;
- To assess Recurrence free survival (RFS);
- To assess potential factors involved in both overall survival and RFS.

METHODS

Study design

Multicenter observational ambispective study.

Population

We will enroll all patients with BCLM underwent liver resection or medical treatment alone afferent to the Fondazione Policlinico Gemelli IRCSS of Rome (Italy), and other 8 International centers (as detailed in the attached document), following the inclusion and exclusion criteria hereafter detailed.

Study duration

The study will overall last 68 months since the approval of the present protocol by the sponsor center institutional review board (IRB), i.e. Fondazione Policlinico Gemelli IRCSS of Rome (Italy), and of all the satellite centers. The prospective enrolment of patients will last till the December 31, 2023 and follow-up phase will last for other 5 years, till December 31, 2028.

Study phases

The study foresees two distinct phases:

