- **I phase (only retrospective phase)** → it will cover all patients underwent to either medical treatment or surgery for which all data are available, with a follow up of 5 years at March 31, 2023. We will retrieve all patients data from January 1994 till March 31, 2018. At the end of “phase I”, we foresee an “ad interim” analysis.
- **II phase (ambispective)** → we will further include all patients retrieved from the archives between April 1, 2018 and the April 30, 2023, as well as all prospectively enrolled patients till December 31 2023, so that the last patient enrolled will end the 5-years follow-up phase within December 31, 2028.

Inclusion criteria

- Age >18 years old;
- Presence of BCLM;
- BCLM and extra-hepatic disease;
- Any treatment;
- Ability to understand and sign the informed consent.

Exclusion criteria

- Inability to provide the informed consent;
- Patients who underwent Best Supportive Care or palliation.

Variables and procedures

The following data will be retrieved from medical archives of each participating center for all retrospectively enrolled patient.

Prospectively enrolled patients' data will instead be collected in the related medical record and reported, alongside all other patients' data, in an electronic dataset protected by password and accessible only to the PI and the co-investigators, and to any other person authorized by PI.

In depth, the following data will be included:

- Anonymized ID;
- Demographic and anthropometric data (e.g., age, sex, BMI, etc..);
- Name of the participating center;
- ER, PR and HER2 status,
- Presence of BRCA1-2 mutation,
- Neoadjuvant-radiotherapy,
- Neoadjuvant endocrine therapy,
- Neoadjuvant-chemotherapy,
- Neoadjuvant-anti-HER2,
- Date of breast surgery,
- Breast tumor T and N,
- Adjuvant radiotherapy,

- Ad-endocrine therapy, Ad-chemotherapy, and Ad-anti-HER2,
- Date of liver metastasis diagnosis,
- Date of liver surgery,
- Liver surgery,
- Liver resection major/minor (Segmental or wedge resection or Left Lateral),
- R status,
- Number of liver metastasis,
- Size of the bigger lesion (mm),
- Distribution (uni or bilobar),
- Postoperative morbidity,
- Hormone receptor expression in the liver metastasis (ER+, PR+),
- Extra-hepatic disease,
- Site of Extra-hepatic disease,
- Mortality and cause;
- Date of death or last FU observation,
- Recurrences,
- Site of recurrences,
- Date of recurrences.

ENDPOINTS

Primary endpoint

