The primary endpoint is to analyze the efficacy of liver surgery as compared to medical therapy alone in terms of 5-years overall survival in patients with breast cancer who underwent to liver resection or medical therapy alone.

Secondary endpoints

- Recurrence rate;
- Post-operative mortality (in patients who underwent to surgical treatment).
- Post-operative complication (in patients who underwent to surgical treatment).
- To assess potential predictive factors of 5-years overall survival in patients with breast cancer who underwent to either liver resection or medical therapy alone.
- To assess recurrence free survival (RFS) of liver surgery as compared to medical therapy alone in terms of 5-years overall survival in patients with breast cancer who underwent to liver resection or medical therapy alone.
- To assess potential predictive factors of 5-years RFS in patients with breast cancer who underwent to either liver resection or medical therapy alone.

STATISTICAL ANALYSIS PLAN

Sample size calculation

The sample size was computed based on the assessment of an improvement in the OS of patients surgically treated as compared to systemic therapy alone.

Based on the evidence from Ruiz and colleagues [10], which reported a 5-years OS of 24% among women treated only with medical therapy and of 69% among those surgically treated, we hypothesize to obtain in our study sample an OS of 60% in the treated group and of 25% in the systemic therapy group.

As such, considering a treatment/control ratio of 0.15/0.85, a two-sided log-rank test with an overall sample size of 117 subjects (99 in the systemic therapy group and 18 in the surgical treatment group) achieves 90% power at a 0,05 significance level to detect a hazard ratio of 0,37 when the proportion of 5-year OS in the control group is 25%. The study will consider a time-window of 30 years of total enrolment (from 1994 to 2023) and a follow-up period of 5 years, for a total time of 35 years. The accrual pattern across time periods is uniform (all periods equal). We expect no subjects drop out both in the control group and treatment groups. The expect no. of events is of 96,5 in the control group and 14,3 in the treatment group. The sample size calculation was performed with PASS2022 v22.0.3 [12,13]. Such sample size estimation is consistent with the disease specific metastasis prevalence and on the no. of involved centers. In fact, we overall expect to include in both retrospective and

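### The data list has no item for drug therapy given for the liver metastases, and the 1994–2023 comparison has no stated adjustment for calendar period

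*Protocol*

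**What the plan says.** The primary objective is to "compare the efficacy of liver resection vs. medical therapy alone in Breast Cancer Liver Metastasis (BCLM) patients", and the primary endpoint is the "efficacy of liver surgery as compared to medical therapy alone in terms of 5-years overall survival". The sample size section sets a "time-window of 30 years of total enrolment (from 1994 to 2023) and a follow-up period of 5 years". The background text before the objectives states: "The primary treatment for BCLM remains chemo-therapy and, more recently, targeted immunotherapy".

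Under Methods, Variables and procedures, the systemic-therapy items are:

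- three neoadjuvant items (chemotherapy, anti-HER2 and "Neoadjuvant endocrine therapy"), listed before the date of breast surgery;
- "Ad-endocrine therapy, Ad-chemotherapy, and Ad-anti-HER2", listed after breast surgery and the breast T and N stage.

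The "Date of liver metastasis diagnosis" comes next. The items after it cover liver surgery, lesion features, morbidity, receptor expression in the metastasis, extra-hepatic disease, death and recurrence. None of them is a drug item.

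Under Statistical analysis, overall survival is estimated by Kaplan-Meier and compared by a log-rank test, with no strata or covariates named. The Cox models take their predictors from univariable p-values and expert opinion. Calendar period is not mentioned.

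**The concern.** The control group is defined by its medical treatment, and the list does not record that treatment. As listed, these patients can be identified only by the absence of liver surgery. The same gap exists in the surgical group, where drugs given for the metastases before or after resection are not captured either. A reader of the results could not tell what surgery was compared with, or whether the two groups had similar drug therapy.

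Patients from 1994 to 2023 are also pooled in one unstratified test, although the background text says that a newer class of treatment has come into use. If the share of patients resected changed over the period and survival on drugs changed too, part of any difference between the groups belongs to calendar period. The bias could favour either group.

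The first gap cannot be left to a later analysis plan, because no analysis can use a variable that was not abstracted from the charts.

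**Working it through.** **Data list.** The neoadjuvant and adjuvant items are tied to breast surgery by their position; the protocol does not say so outright. Suppose instead that they referred to liver surgery. Both terms are defined relative to an operation, so they still could not describe patients who had no liver operation. On either reading, the treatment of the group planned as 85% of patients (treatment/control ratio 0.15/0.85) is unrecorded.

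**What can be derived.** Date of liver metastasis diagnosis, ER, PR and HER2 status, and centre are listed for all patients. Calendar period is therefore available in both groups. The regimen received is not.

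**The plan's own figure.** The planned hazard ratio is ln(0.60)/ln(0.25) = 0.368, stated as 0.37. It reproduces and is not in dispute. It is used below only as a yardstick.

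**Size of possible confounding by period, surgery having no effect.** The protocol expects about 500 patients in the retrospective phase out of 675–720, which leaves 175–220; I use 500 early and 200 late. Assumed, not from the protocol: 5-year survival of 15% early and 35% late in both treatment groups, and the resected shares shown.

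Resected survival = (500·p₁·0.15 + 200·p₂·0.35)/(500·p₁ + 200·p₂), where p₁ and p₂ are the early and late resected shares. Medical survival uses 1−p₁ and 1−p₂. Apparent HR = ln(resected)/ln(medical), a summary at 5 years.

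| Resected share, early / late | Resected 5-year OS | Medical 5-year OS | Apparent HR |
|---|---|---|---|
| 5% / 25% | 21.25/75 = 28.3% | 123.75/625 = 19.8% | 0.78 |
| 10% / 20% | 21.5/90 = 23.9% | 123.5/610 = 20.2% | 0.90 |
| 25% / 5% | 22.25/135 = 16.5% | 122.75/565 = 21.7% | 1.18 |

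Within each period the two groups have the same survival by construction, so an analysis stratified by period would return a hazard ratio of 1 in all three rows.

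**Second set of assumptions, tied to the planned control rate.** Hold medical 5-year survival at the protocol's 25%. Assume that 40% of medical and 60–80% of surgical patients fall in a modern drug period, with a modern-versus-old hazard ratio h of 0.5–0.8. Solve 0.4·s^h + 0.6·s = 0.25 for old-period survival s. Surgical survival is then q·s^h + (1−q)·s, where q is the surgical group's modern share.

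- h = 0.5, q = 0.8: s = 0.155, surgical survival 34.5%, HR = ln(0.345)/ln(0.25) = 0.77.
- h = 0.8, q = 0.6: surgical survival 26.6%, HR 0.96.

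**The case against.** A reader might infer that surgery cannot be separated from drug era at all, or that the comparison cannot be interpreted for any period. The protocol does not support that. The diagnosis date is collected for everyone, so period can be derived and used for stratification or adjustment, together with receptor status and centre. What cannot be separated is surgery from the drugs a patient actually received.

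Several further objections have force:

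- The hazard ratios above measure confounding by calendar period, which a date already on the list can address. They do not measure the harm from missing drug data, for which the protocol gives no figure.
- The inputs are assumed. In the first set, medical survival comes out at 20–22% against the planned 25%, and the overall resected share at 11%, 13% and 19% (75, 90 and 135 of 700) against the planned 15%. The early/late split is a boundary between study phases, not a date at which drugs changed.
- The background sentence on immunotherapy carries no dates and does not say how many study patients are affected.
- Choosing predictors partly by expert opinion leaves room for period in the Cox model, and a separate analysis plan could specify it.

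The last objection weakens the adjustment part of the point but does not remove it. The protocol does fix the method of the primary comparison, and that method is unstratified. The objection does not touch the data-list gap.

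**Conclusion.** The point holds in two parts. First, the variable list contains nothing on systemic therapy given for the liver metastases, so the comparator cannot be described or adjusted by regimen. This rests on reading the neoadjuvant and adjuvant items as belonging to breast surgery, but the other reading leaves the medical group just as undescribed. Second, calendar period is derivable, yet the primary comparison as written does not use it.

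The size of the first part cannot be computed from the protocol. For the second, apparent hazard ratios of 0.78 to 1.18, or 0.77 to 0.96 under the second set of assumptions, are hypothetical and depend on assumed survival rates, period shares and resection shares. Imbalance of that order would bias the estimate but would not by itself produce the planned 0.37.

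**What to change.** 1. Stratify the surgery-versus-medical log-rank test and Cox comparison by period of liver metastasis diagnosis, with cut-points fixed before the data are analysed. Report period-specific estimates, including one for recent patients, so that the conclusion refers to an identifiable comparator.
2. Add yes/no items, for both groups, for the class of systemic therapy given for the liver metastases: chemotherapy, endocrine, anti-HER2, and immunotherapy or other targeted therapy. In the surgical group, separate therapy before resection from therapy after it. Therapy after resection is post-baseline and may be part of the surgical strategy, so use it for description and not as an adjustment covariate.

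The stratification needs no new data. Its price is wider intervals within periods: 15% of 675–720 is about 101–108 resected patients in all, or roughly 34–36 per period if three equal groups were used (an assumption). The new items need some extra chart abstraction at each centre, and the oldest records will have unknown entries, which should be coded as unknown rather than as not given.

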prospective phase 75-80 patients/center, for overall sample of 675-720 patients. Particularly, the retrospective phase, which will include patients till 2017 will consist of about 500 patients, already consistent with the sample size estimate provided, whilst the other will pertain to the period 2018-2023.

Statistical analysis

The sample will be described in its clinical and demographic characteristics by descriptive statistics techniques. In depth, qualitative data will be expressed as absolute and relative percentage frequency, whilst quantitative variables either by mean and standard deviation (SD) or median and interquartile range (IQR), as appropriate. To verify the Gaussian distribution of quantitative variables, the Shapiro-Wilk test will be applied.

Missing values, as <5% in all cases, were treated by *imputeR* package, using multiple imputation with Lasso Regression methods centered on the mean as for quantitative data, whilst classification trees for imputation by “rpartC” function, centered on the mode, i.e. most represented class object, were applied on qualitative data [14].

Between groups differences were analyzed by either the Chi squared test or the Fisher-Freeman-Halton test for qualitative data, whilst either the Student’s t test or non-parametric Mann-Withney U test will be applied on quantitative data, as appropriate.

Differences between groups will be further exemplified by clustered violin plots or plots describing pre-post variation in individual groups. Such plots will be produced with the R packages “ggplot2”, “ggstatsplot”, “ggpubr”, “ggprism”, and “ggsignif” [15-19].

OS will be calculated from the date of treatment initiation through the date of death from any cause; subjects alive at the last follow-up will be censored. Overall survival and RFS probabilities at 5 years will be estimated using the Kaplan Meier method and compared by the log-rank test. The KM curve will also be reported. The analysis will be performed with the R package “*ggplot2*” and “*survminer*” R packages [15,20].

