To assess potential prognostic factors of 5-year RFS and OS, both univariable and multivariable Cox proportional hazards regression models will be fitted, and hazard ratios (HR) and 95% confidence intervals (CI) consequently reported. The proportionality of the hazards will be assessed by visual inspection of the hazards and Schoenfeld residuals. In case of doubtful proportionality, Cox weighted regression models will be fitted. “*survival*” and “*coxphw*” R packages will be used for the whole analysis [21-24]. The predictors to be included in the multivariable model will be selected on the basis of univariable analysis ($p < 0.05$ or suggestive, i.e. $0.05 \leq p < 0.10$) and expert opinion, also considering the possibility of overcoming the rule of 10 events per variable (EPV) [25,26]. Statistical significance will be set at a p-value < 0.05 . Suggestive p-values will be further reported ($0.05 \leq p < 0.10$). All analyses will be performed with R software version 4.2.0 (CRAN ®, R Core 2022) [27].

References

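### RFS is compared between resected and medically treated patients, although no disease-free state is required and no listed data item records response, remission or progression

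*Protocol*

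**What the plan says.** **Endpoints.** Protocol, Secondary endpoints, sets an RFS contrast between the two treatments: "To assess recurrence free survival (RFS) of liver surgery as compared to medical therapy alone in terms of 5-years overall survival". A further endpoint is "To assess potential predictive factors of 5-years RFS in patients with breast cancer who underwent to either liver resection or medical therapy alone". Under Secondary Objectives, a recurrence rate is wanted after either treatment.

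**Analysis.** Protocol, Statistical analysis: "Overall survival and RFS probabilities at 5 years will be estimated using the Kaplan Meier method and compared by the log-rank test". The same section adds: "To assess potential prognostic factors of 5-year RFS and OS, both univariable and multivariable Cox proportional hazards regression models will be fitted". For overall survival it gives an origin and an event: "OS will be calculated from the date of treatment initiation through the date of death from any cause".

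**Population.** Protocol, Inclusion criteria, asks for "Presence of BCLM" and also lists "BCLM and extra-hepatic disease"; treatment is unrestricted. The exclusions are inability to consent and best supportive care or palliation.

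**Data.** Protocol, Variables and procedures, lists recurrences with their site and date, R status, and extra-hepatic disease with its site.

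**The concern.** Recurrence presupposes that disease has gone. After complete resection with no disease elsewhere, there is a point from which a patient can be free of recurrence. A patient on systemic therapy with liver metastases still present generally has no such point; what can be observed is progression or death. A log-rank test of RFS between these groups then sets relapse after resection against progression of unresected disease. A Cox model for RFS across both groups mixes the same two events, so its hazard ratios have no single meaning.

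At stake is how the secondary results are read. A difference in RFS curves would naturally be reported as surgery reducing, or not reducing, recurrence, and the planned data could not support either statement.

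**Working it through.** The protocol states no figure for RFS, so there is none to reproduce. The check is a reading of the relevant sections against each other, with simple counts.

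1. **Is the comparison fixed by the protocol?** Yes. The endpoint names both treatments, and the analysis section applies Kaplan-Meier and log-rank to RFS together with OS. The predictor endpoint covers patients who had either treatment. It does not say whether the groups are modelled together or separately; fitted separately, the medical model would still lack a disease-free origin.

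2. **Is anyone required to be disease-free?** No. Liver metastases are an entry condition, extra-hepatic disease appears among the inclusion criteria, and neither R0 resection nor complete response is asked for, at entry or for the RFS analysis.

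3. **Could the listed data identify a disease-free state?** Counting the bullets under Variables and procedures:
   - Items in total: 30.
   - Dates: 5 (breast surgery, liver metastasis diagnosis, liver surgery, death or last follow-up, recurrences). The date of liver surgery cannot exist for a patient treated medically alone, so 5 − 1 = 4 can apply there, including the date of recurrences.
   - Items recording response, remission or progression: 0.
   - Items bearing on clearance: R status describes a resection and stands directly after the resection items, so it is safe to infer that it exists only for resected patients. Extra-hepatic disease is listed for everyone, but has no time point and says nothing about whether the liver lesions are gone.

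   Clearance can therefore be approximated in resected patients from R status and extra-hepatic disease. In medically treated patients it cannot be identified, even in one who had a complete response.

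4. **What would the event be?** In a resected, cleared patient: relapse. In a resected patient who was not cleared, or a medically treated patient with metastases in place: generally progression, if the centre entered it under recurrences.

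5. **Which way would the result move?** If centres enter progression under recurrences, the medical group accrues events that are not recurrences and looks worse. If they leave the field blank because nothing has recurred, it looks better. The protocol does not say which practice applies, so the direction is open.

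6. **How much of the plan is touched?** Three of the six secondary endpoints (recurrence rate, RFS comparison, RFS predictors) and all three secondary objectives, the third only for its RFS part.

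**The case against.** **Definitions belong in a statistical analysis plan.** The RFS origin, event and analysis set may be fixed in a plan not shown here. This stands: the absence of an RFS origin beside the OS origin is not counted as a fault, and entry criteria that admit active disease are natural in a study whose primary endpoint is OS. What remains is that the protocol itself fixes a two-group RFS comparison in this population.

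**The recurrence items could hold progression.** They are listed without restriction to resected patients, and a data dictionary could code progression under them. This also stands, so a reader should not infer that the medical group has no usable event data. But an event coded that way is progression, and the endpoint would have to be named and defined as such.

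**Stronger readings that the document does not support.** A reader might infer that:
- part of the surgical group relapses after incomplete clearance. No proportion of incomplete resections is given;
- recurrence rates are to be tested between groups. Only a recurrence rate is named, and a test would have to be inferred from the general between-group methods;
- the planning split, "99 in the systemic therapy group and 18 in the surgical treatment group", measures the damage. It gives 99/117 = 84.6% medical patients, but it was set for OS, is not applied to the 675–720 patients expected, and says nothing about RFS distortion.

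**Restricting to cleared resected patients is only one remedy.** This is fair. If the criterion "BCLM and extra-hepatic disease" is read as a requirement, a set without extra-hepatic disease could be empty. The criterion must be clarified first, and a renamed progression endpoint is a legitimate alternative.

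**Conclusion.** The point holds. As written, the RFS log-rank comparison and the RFS predictor models across both treatments do not concern the same event in the two groups and cannot be interpreted as effects on recurrence. This is a fault in a comparison that the protocol prescribes, and goes beyond a detail left for later.

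Neither the size nor the direction of any distortion can be derived from the document, and none is claimed. The conclusion rests on two assumptions: that R status exists only for resected patients, and that metastases generally remain in place under medical therapy alone. The RFS endpoint's wording is a separate, smaller defect, since it expresses RFS in terms of overall survival.

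Only secondary endpoints are affected. Primary OS runs to death from any cause and needs no disease-free state. The correction should be made, but the study's main question does not depend on it.

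**What to change.** 1. Drop the between-group RFS comparison and keep OS as the between-group outcome.
2. State whether the extra-hepatic inclusion criterion admits or requires such disease.
3. If it admits it, report recurrence rate, RFS and RFS predictors only in resected patients rendered disease-free (R0, no known extra-hepatic disease at liver surgery), timed from the date of liver surgery. The items needed are already listed; extra-hepatic disease must be recorded as status at liver surgery.
4. Alternatively, if a between-group disease-control endpoint is wanted, name it progression-free survival. Give it one event definition and one explicit origin in both groups, saying whether treatment initiation in resected patients means systemic therapy or surgery. Use it only if progression dates can be retrieved comparably across the nine centres and the archive years back to 1994.
5. Delete the reference to five-year overall survival from the RFS endpoint.

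**Cost.** Three secondary endpoints, the secondary objectives and the RFS sentences in the analysis section need rewording. One secondary between-group comparison is lost or renamed. Under step 3 the RFS set becomes a surgical subset of unknown size. The protocol's background calls isolated liver metastases rare in breast cancer, so that subset may be small and support few predictors. Step 4 needs progression dates and a start date for medical therapy. Neither is listed, although OS already needs the second.

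### Missingness below 5% is stated as fact before the data are in, and the fill labelled multiple imputation is a best guess that would dilute prognostic-factor hazard ratios if missingness were well above 5%

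*Protocol*

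**What the plan says.** The missing-data rule is in the protocol, Statistical Analysis Plan, Statistical analysis. It begins "Missing values, as <5% in all cases, were treated by" the imputeR package. Quantitative data are handled "using multiple imputation with Lasso Regression methods centered on the mean as for quantitative data". For qualitative data, classification trees (rpartC) are used, "centered on the mode, i.e. most represented class object, were applied on qualitative data".

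The data were not yet in hand. Variables and procedures says: "The following data will be retrieved from medical archives of each participating center for all retrospectively enrolled patient". Study phases has retrieval reaching back to January 1994, and phase II adds later archive patients "as well as all prospectively enrolled patients till December 31 2023". Follow-up runs to the end of 2028.

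Imputed covariates enter the univariable and multivariable Cox models for prognostic factors of 5-year OS and RFS. Those models also screen predictors by univariable p-value. The comparison of OS and RFS between groups is by Kaplan-Meier and log-rank, without covariates.

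**The concern.** Two things are fixed badly in the printed text. First, a missingness rate is asserted for every variable before it can be observed, and the whole approach leans on it. Second, the name of the method and its description disagree. Multiple imputation draws several plausible values and carries their spread into the standard error. A value centred on the mean or on the commonest class is a single best guess.

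The secondary endpoints on predictive factors of OS and RFS are at stake. Guessing the commonest class for a categorical factor misclassifies some patients and pulls that factor's hazard ratio towards 1. The filled values then count as observed, both in the confidence intervals and in the p-value screen that decides which factors enter the multivariable model.

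**Working it through.** **1. The stated figure.** The value below 5% has no inputs or source in the protocol, so it cannot be reproduced. The timing in Study phases shows that it cannot have been observed for the whole sample.

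**2. Could it still turn out true?** Phase I is limited to patients with all data available. The protocol expects about 500 retrospective patients up to 2017 within a total of 675-720. If those 500 had no missing values at all, a variable would stay below 5% overall as long as phase II missingness did not exceed:
- total 675: 0.05 × 675 = 33.75, and 33.75 / (675 − 500) = 19.3%
- total 720: 0.05 × 720 = 36, and 36 / (720 − 500) = 16.4%

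So the figure is possible, but it rests on one reading of an ambiguous phrase. Even then the pooled rate could hide 16-19% missing in phase II.

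**3. Label against method.** With M imputations, Rubin's total variance is T = W + (1 + 1/M)·B, where W is the average within-imputation variance and B the variance between imputations. If each missing value is replaced by the same best guess, B = 0 and T = W. No imputation uncertainty is carried forward.

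**4. Effect on a categorical factor.** All inputs here are assumed except the sample size and the allocation ("treatment/control ratio of 0.15/0.85"). N = 700, 15% resected, true surgery HR 1.00, factor HR 0.50, factor present in 75% of resected and 50% of medical patients, values missing only in medical patients, one observed proxy for the tree-like fill, 500 cohorts per row. Cells show surgery HR / factor HR.

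| Missing in medical arm | Plain mode fill | Tree-like class fill | Complete case |
|---|---|---|---|
| 5% | 0.97 / 0.51 | 0.99 / 0.51 | 0.99 / 0.50 |
| 20% | 0.93 / 0.55 | 0.99 / 0.54 | 1.01 / 0.50 |
| 40% | 0.87 / 0.60 | 0.97 / 0.58 | 1.00 / 0.50 |
| 40%, value-dependent | 0.83 / 0.63 | 0.92 / 0.58 | 1.00 / 0.50 |

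A smaller check with 60 cohorts per level gave tree-like factor HRs of 0.51, 0.53 and 0.57 at 5, 20 and 40%. Multiple imputation and complete-case analysis stayed near 0.50.

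Share of the log hazard ratio lost = 1 − ln(HR) / ln(0.50):
- tree-like, 20%: 1 − ln 0.54 / ln 0.50 = 11% (8% with 0.53)
- tree-like, 40%: 1 − ln 0.58 / ln 0.50 = 21% (19% with 0.57)
- plain mode, 20% and 40%: 14% and 26%

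**5. Effect on the surgery HR, continuous confounder.** Assumed: N = 700, about 15% surgery, surgery HR ln 0.60 / ln 0.25 = 0.368, confounder HR 1.82 per SD, correlation 0.4 with an observed covariate, log-odds of surgery −0.8 per SD, 150 runs. Cells show the adjusted surgery HR divided by its full-data value.

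| Missing, surgery / medical | Mechanism | Mean fill | Regression fill | Multiple imputation | Complete case |
|---|---|---|---|---|---|
| 0% / 5% | arm only | 0.998 | 1.002 | 0.999 | 1.001 |
| 0% / 5% | value-dependent | 0.978 | 0.984 | 0.984 | 1.001 |
| 5% / 20% | arm only | 0.980 | 1.014 | 0.998 | 0.995 |
| 5% / 20% | value-dependent | 0.918 | 0.952 | 0.952 | 0.995 |
| 5% / 40% | arm only | 0.960 | 1.016 | 0.990 | 0.998 |
| 5% / 40% | value-dependent | 0.841 | 0.875 | 0.880 | 1.000 |

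In the 5% / 40% arm-only case the confounder's own HR was 1.832 with full data, 1.819 with regression fill and 1.735 with mean fill. The dilution is therefore mainly a matter of class fill for categorical factors, or of a literal mean fill.

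**The case against.** The strongest reply is that little follows if the stated rate holds. That stands: up to 5% missing, the surgery HR moves by about 2-3% at most and the factor HR from 0.50 to 0.51. The past tense is also weak evidence by itself, since the next paragraph of the section uses it too for planned group comparisons.

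A reader might infer several stronger things that the protocol does not support:
- **That differential missingness by arm alone biases the surgery HR.** With regression fill that includes arm, the ratio stays at 1.00-1.02 even at 5% against 40% missing. The protocol names Lasso and tree predictions, and its wording does not prove an unconditional mean or mode fill.
- **That the plan's own figures contradict the 5%.** R status, resection type, date of liver surgery and postoperative morbidity do not apply to unoperated patients. They are not missing values, and nothing says they would be imputed.
- **That receptor status of the metastasis is missing mainly in medical patients.** This is plausible, because resection yields tissue, but the protocol gives no availability by arm. It remains an assumption.
- **That pooling and the outcome are left out of the imputation.** The protocol is silent, and these details may sit in a statistical analysis plan that is not shown. Their absence is not counted.
- **That the group comparison of OS is compromised.** It uses no covariates. It would be touched only if dates or vital status were imputed, which the text neither says nor excludes.

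It is also fair that multiple imputation does not cure value-dependent missingness: at 5% / 40% it gives 0.880 against 0.875 for regression fill. Complete-case analysis gave 1.000 in that setting, which is why it belongs in the fix.

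**Conclusion.** The point holds in a limited form. The 5% is an unsupported assumption written as fact, with no rule if it is exceeded, and the method's label does not match its description. Below 5% the consequence is negligible. At an assumed 20-40% missing in the medical arm, a categorical factor's HR of 0.50 is reported as about 0.53-0.58 under tree-like fill (8-21% of the log HR lost) and 0.55-0.60 under plain mode fill (14-26% lost), and guessed values count as observed.

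The adjusted surgery HR shifts materially only with a literal mean or mode fill (down to 0.87 for a true 1.00) or with value-dependent missingness (5-16% in favour of surgery in the continuous setting, 8-17% in the binary one). The Kaplan-Meier and log-rank comparison stands apart from this.

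The missingness levels, factor effects and mechanisms are all assumptions. The continuous simulation has 150 runs per scenario and the smaller binary check 60, so differences of a point or two mean little.

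**What to change.** In the protocol's Statistical analysis section:
- Restate the 5% as an expectation, and report missingness per variable and treatment arm.
- Replace the imputeR best-guess fill, for covariates in the Cox models, with genuine multiple imputation: several random draws, treatment and outcome (event indicator and cumulative hazard) in the imputation model, and pooling by Rubin's rules. Use it whatever the observed rate, so that no separate fallback is needed.
- State that surgery-only fields are not applicable in medical patients and are not imputed.
- Add a complete-case Cox analysis as a sensitivity analysis, since multiple imputation alone does not protect against value-dependent missingness.

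The cost is a wording change, a little more programming in the same software, and slightly wider confidence intervals. No further data are needed.
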